### **6.3.2 Visit 3 (Day 57 [Window: Days 57-63]) Follow-up**

- Medical history will be reviewed and updated as appropriate.
- Interim sexual history since the last clinic visit will be collected.
- Vaginal symptoms will be assessed.
- A urine pregnancy test will be performed on all participants of childbearing potential.
- Compliance with the study protocol criteria will be assessed; all used and unused study IP packaging will be collected as relevant and recorded.
- Participant memory aid will be collected and reviewed.
- All concomitant medications taken since V2 will be recorded on the appropriate DCF. Previously recorded medications will be updated as appropriate.

---

- Study personnel will discuss with participants and assess and record all AE/SAEs. Previously recorded AE/SAEs will be updated as appropriate.
- If clinically indicated, a targeted physical examination will be performed by a qualified study clinician.
- A pelvic examination to include examination of external genitalia will be conducted, and swabs and samples taken for analysis of Amsel criteria; KOH and saline microscopy for identification of yeast forms, trichomonas, and clue cells; Gram staining; the BD Max test; and for future analysis, for participants who consented to future use of their specimens. Instructions for obtaining vaginal swab specimens for these assessments are outlined in the protocol specific MOP. Gram stain Nugent scoring will be conducted in the Central Laboratory; all other testing will be conducted locally.
- Participants with clinical evidence of VVC based on vulvovaginal signs (edema, erythema, and/or excoriation) and symptoms (vulvovaginal itching, burning, and/or irritation) will have a confirmatory vaginal *Candida* culture and treated as appropriate with oral fluconazole. Participants who cannot take oral fluconazole will be terminated from the study.
- Vulvovaginal signs will be assessed and graded by severity, as applicable. A clinical determination for BV recurrence will be made based on evaluation of Amsel criteria. The presence of  $>2$  of 4 Amsel criteria is required for a diagnosis of BV recurrence. Participants with a clinical diagnosis of BV recurrence will complete a satisfaction questionnaire and will be terminated from the study.
- Participants who are negative for BV recurrence determined as  $\leq 2$  of 4 Amsel criteria will be scheduled for the next return visit, blinded IP and memory aid will be provided, and protocol requirements and dosing instructions reviewed. Participants will be counseled to refrain from receptive oral, anal, and vaginal sexual intercourse 24 hours prior to the next study visit, as this can affect the accuracy of vaginal pH measurement.
- Study staff will contact participants as a reminder for Visit 4 and to discuss adherence to IP and any barriers to IP use.

### **6.3.3 Visit 4 (Day 85 [Window: Days 85-91]) Follow-up (TOC)**

- Medical history will be reviewed and updated as appropriate.
- Interim sexual history since the last clinic visit will be collected.
- Vaginal symptoms will be assessed.

---

- A urine pregnancy test will be performed on all participants of childbearing potential.
- Compliance with the study protocol criteria will be assessed; all used and unused study IP packaging will be collected as relevant and recorded.
- Participant memory aid will be collected and reviewed.
- All concomitant medications taken since V3 will be recorded on the appropriate DCF. Previously recorded medications will be updated as appropriate.
- Study personnel will discuss with participants and assess and record all AE/SAEs. Previously recorded AE/SAEs will be updated as appropriate.
- If clinically indicated, a targeted physical examination will be performed by a qualified study clinician.
- A pelvic examination to include examination of external genitalia will be conducted, and swabs and samples taken for analysis of Amsel criteria; KOH and saline microscopy for identification of yeast forms, trichomonas, and clue cells; Gram staining; BD Max test; and for future analysis, for participants who consented to future use of their specimens. Instructions for obtaining vaginal swab specimens for these assessments are outlined in the protocol specific MOP. Gram stain Nugent scoring will be conducted in the Central Laboratory; all other testing will be conducted locally.
- Participants with clinical evidence of VVC based on vulvovaginal signs (edema, erythema, and/or excoriation) and symptoms (vulvovaginal itching, burning, and/or irritation) will have a confirmatory vaginal *Candida* culture and treated.
- Vulvovaginal signs will be assessed and graded by severity, as applicable. A clinical determination for BV recurrence will be made based on evaluation of Amsel criteria. The presence of >2 of 4 Amsel criteria is required for a diagnosis of BV recurrence.
- Participant will complete a satisfaction questionnaire.

#### **6.3.4 Early Termination Visit**

The V4 assessments and DCFs (see [Section 6.3.3](#)) must be completed at the early termination visit for participants who withdraw, or are withdrawn, or terminated from the study. If a participant withdraws between scheduled visits, the participant will be asked to return to the clinic to perform the V4 assessments.

## 6.4 Unscheduled Study Visits

Unscheduled visits may occur at any time during the study. For example, for problems with the study medication or development of intercurrent vaginal symptoms. Any of the following activities will be performed at the discretion of the site PI:

- Medical history will be reviewed and updated as appropriate.
- Interim sexual history since the last clinic visit will be collected.
- Vaginal symptoms will be assessed.
- A urine pregnancy test will be performed on all participants of childbearing potential.
- Compliance with the study protocol criteria will be assessed; any used and unused study IP packaging will be collected as relevant and recorded.
- Participant memory aid will be collected and reviewed.
- All concomitant medications taken since the last study visit will be recorded on the appropriate DCF. Previously recorded medications will be updated as appropriate.
- Study personnel will discuss with participants and assess and record all AEs/SAEs. Previously recorded AEs/SAEs will be updated as appropriate.
- If clinically indicated, a targeted physical examination will be performed by a qualified study clinician.
- A pelvic examination to include examination of external genitalia will be conducted, and swabs and samples taken for analysis of Amsel criteria; KOH and saline microscopy for identification of yeast forms, trichomonas, and clue cells; and Gram staining. Instructions for obtaining vaginal swab specimens for these assessments are outlined in the protocol specific MOP. Gram stain Nugent scoring will be conducted in the Central Laboratory; all other testing will be conducted locally.
- Participants with clinical evidence of VVC based on vulvovaginal signs (edema, erythema, and/or excoriation) and symptoms (vulvovaginal itching, burning, and/or irritation) will have a confirmatory vaginal *Candida* culture and treated as appropriate with oral fluconazole. Participants who cannot take oral fluconazole will be terminated from the study.
- Vulvovaginal signs will be assessed and graded by severity, as applicable. A clinical determination for BV recurrence will be made based on evaluation of Amsel criteria. The

---

presence of  $>2$  of 4 Amsel criteria is required for a diagnosis of BV recurrence. Participants with a clinical diagnosis of BV recurrence will complete a satisfaction questionnaire and will be terminated from the study.

- Participants who are negative for BV determined as  $\leq 2$  of 4 Amsel criteria will be scheduled for the next return visit, blinded IP and a memory aid will be provided as needed, and protocol requirements and dosing instructions reviewed.

## 6.5 Protocol Deviations

A protocol deviation (PD) is any noncompliance with the clinical trial protocol, GCP, or MOP requirements. The noncompliance may be either on the part of the participant, the investigator, or the study site staff. As a result of deviations, corrective actions should be developed by the site and implemented promptly

These practices are consistent with ICH E6:

- 4.5 Compliance with Protocol, Sections 4.5.1, 4.5.2, and 4.5.3
- 5.1 Quality Assurance and Quality Control, Section 5.1.1
- 5.20 Noncompliance, Sections 5.20.1, and 5.20.2.

It is the responsibility of the site PI and other study staff to use continuous vigilance to identify and report deviations within 5 working days of identification of the PD, or within 5 working days of the scheduled protocol-required activity. All deviations must be promptly reported to DMID, via the SDCC's electronic study database.

NOTE: Those sites participating in trials with a designated "central unit" will follow the reporting requirements specified in their protocols and MOPs. The "central unit" will be responsible for submission of the PD to TRI/ICON DMID CROMS.

All PDs, as defined above, must be addressed in study participant DCFs. A completed copy of the DMID PD Form must be maintained in the Regulatory File, as well as in the participant's study folder. PDs must be submitted to the central IRB/IEC and to the local IRB/IEC per their guidelines. The site PI and other study staff are responsible for knowing and adhering to their IRB requirements.

---

## 7 DESCRIPTION OF CLINICAL AND LABORATORY EVALUATIONS

### 7.1 Clinical Evaluations

Complete medical history will be obtained by interview of the participants at V0 and will be updated at each clinic visit. At follow-up visits, an interim medical history will be obtained by interview of the participants noting any changes since the previous visit.

Sexual history will be obtained by interview of the participants at V0. Participants will be queried at V1 thru V4 regarding sexual activity since the previous clinic visit.

Medications history (concomitant medications) will include a review of all current medications taken 30 days prior to the screening visit and through study completion. Prescription and over-the-counter drugs will be included as well as vitamins, herbs and supplements. Assessment of eligibility will also include a review of all permitted and prohibited medications per the Participant Inclusion and Exclusion Criteria (see [Section 5](#)).

A pelvic examination including examination of external genitalia, will be performed at the screening visit, V0. A targeted physical examination including height and weight will be performed at enrollment visit, V1, and if clinically indicated for follow-up visits, and pelvic examination will be performed at the enrollment visit, V1, and at each of the follow-up visits, V2 thru V4. All physical examinations will be performed by a qualified study clinician.

Study IP, memory aids and instructions will be provided to participants at the enrollment visit, V1 and return visits, V2 and V3. Compliance with the study IP will be assessed at all follow-up visits and contacts (V2-V4 and as needed at unscheduled and early termination visits) and recorded.

A pelvic examination and vulvovaginal examination for the evaluation of the vulva, vagina, and cervix will be performed by the site PI or qualified designee. At the screening visit, V0, these examinations will be done for the purpose of determining eligibility. At the enrollment visit, V1, Follow-up visits (V2-V4), or an unscheduled visit these examinations will be done for the purpose of evaluating treatment efficacy and the presence of treatment-emergent AEs (TEAEs).

#### **Pelvic Examination:**

During the initial screening visit, V0 pelvic examination, the clinical diagnosis of BV will be based on the presence of 3/4 of the following Amsel criteria:

---

1. Homogenous vaginal discharge characteristic of BV;
2. A fishy odor of the vaginal discharge with the addition of a drop of 10% KOH (positive whiff test);
3. Clue cells  $\geq$  20% of the total vaginal squamous epithelial cells on saline microscopy;
4. Vaginal fluid pH  $>4.5$ .

Instructions for obtaining and determining the presence of Amsel clinical criteria can be found in the protocol-specific MOP.

During the enrollment visit's, V1 pelvic examination, a clinical determination to confirm BV cure following metronidazole or CDC-recommended BV treatment induction will be determined by  $\leq$  2 of 4 Amsel criteria and absence of BV symptoms (defined as absence of homogenous discharge and odor).

At all other follow-up visits on suppressive study IP (V2-V4), a clinical determination of BV recurrence will be determined as  $>$  2 of 4 Amsel criteria by pelvic examination.

For the enrollment V1 or follow-up (V2 – V4) visits, participants will be scheduled outside of menses as soon as possible after cessation of menstruation.

At all follow-up visits (V2-V4), a clinical diagnosis of VVC will be based on vulvovaginal signs (edema, erythema, and excoriation) and symptoms (itching, burning, and irritation) and a positive KOH microscopy with identification of yeast forms (hyphae/pseudohyphae) or budding yeasts. A confirmatory Candida culture with speciation will also be performed; Candida culture in the setting of incomplete criteria for the clinical diagnosis may be obtained at the discretion of the study clinician.

### **7.1.1 Assessment of Concomitant Medications/Treatments other than Study Product**

Administration of any medications, therapies, or vaccines will be recorded on the appropriate DCF. Concomitant medications will include all medications taken 30 days prior to the initial screening visit V0, through V4 or early termination, whichever occurs first. Prescription and over-the-counter drugs will be included, as well as herbs, vitamins, and supplements.

Participants who have received study IP and are subsequently diagnosed with a concomitant infection that requires systemic antibiotics will receive treatment according to the local clinic's standard protocols but will be considered non-evaluable for efficacy and terminated from the study. However, participants who have received study IP and are subsequently diagnosed with VVC can remain in the study and be considered evaluable for efficacy if they are appropriate candidates for oral fluconazole therapy.

---

At the discretion of the site PI, use of new medication should prompt evaluation for the presence of a new diagnosis of chronic medical disease or condition.

Medications that might interfere with the evaluation of the IP should not be used unless absolutely necessary.

Refer to [Section 5](#) (Selection of Participants and Study Enrollment and Withdrawal) for medications that are prohibited for study eligibility and throughout study participation.

### **7.1.2      Assessment of Participant Compliance with Study Intervention/Investigational Product**

The TOL-463 Insert and placebo are inserted by the study participant.

At each follow up visit, V2 through V4, participants will be asked to bring the study IP packaging, unused inserts (if any) and memory aid corresponding to the return visit (V2, V3 or V4) to the study personnel. Study personnel will review adherence to the study IP schedule with the participants, including the participant memory aid, and record this on the appropriate DCF at each follow-up visit and any unscheduled visits. Study personnel will record the number of unused inserts and empty packaging returned at each of the follow-up visits, V2 thru V4.

Compliance with the study protocol will be assessed and documented by study personnel at each of the follow-up visits, V2 thru V4, and at any unscheduled visits. Study personnel may discard the participant's memory aid after documenting compliance. Refer to 4.4 for instructions on handling of returned study IP packaging.

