Laboratory testing will include urine pregnancy, nucleic acid amplification tests (NAATs) for chlamydia, gonorrhea, and trichomoniasis, and Gram stain for Nugent scoring, as well as assessment of vaginal pH, saline microscopy (clue cells, motile trichomonads, yeast forms), and

---

KOH preparation at each site's local lab. *Candida* culture will be performed as clinically indicated. Polymerase Chain Reaction, PCR-based molecular diagnosis of BV through a multi-organism PCR algorithm on the BD Max Vaginal Panel will be performed at a certified laboratory for all scheduled study visits.

The duration of the study for participants who are enrolled and randomized will be approximately 100 days. For those not enrolled, participation will end at their V1, Day 1. Enrollment is expected to be completed in approximately twenty four months.

All participants will be asked to abstain from anal, receptive oral, and vaginal sexual intercourse within one hour of IP administration and for 24 hours after. Participants who are sexually active will be required to use an effective form of birth control during study participation through the final visit/V4. A simplified participant memory aid will be provided to study participants to document symptoms, AEs, and protocol compliance.

For additional details on study procedures and evaluations and study schedule by study visits, see [Sections 6](#) and [7](#) and [Appendix A](#)

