#### **3.3.2 Secondary Endpoints**

1. Time to BV recurrence.
2. Proportion of participants reporting BV symptoms through the follow-up period.
3. Number of participants satisfied with the study treatment through the follow-up period.
4. The occurrence of AEs considered product-related following initiation of study treatment and through the final study visit.
5. The occurrence of culture confirmed secondary VVC following initiation of study treatment and through the final study visit.

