#### **10.5.4.2 Secondary Efficacy Analyses**

The secondary efficacy analyses are briefly described below. Secondary efficacy analyses will be performed in the mITT and PP analysis populations, where appropriate. Details of these analyses and any sensitivity analyses will be specified in the separate SAP document.

For the analysis of Secondary Objective 1, the median time to BV recurrence will be estimated by treatment group using Kaplan-Meier estimates. For participants who experience BV recurrence by V4, the time of BV recurrence will be defined as the midpoint between the earliest time point of a positive BV diagnosis (post-baseline) and the previous observed time-point. For participants without BV recurrence at or before V4, the BV recurrence endpoint will be coded as censored, with time to recurrence defined as the elapsed time from the first dose of IP, to the earliest of: V4 time-point, the last observed time-point prior to loss to follow-up, or the time-point at which the participant became ineligible for the particular analysis population.

For the analysis of Secondary Objective 2, the proportion of participants experiencing vaginal symptoms as assessed by the participant via the daily memory aid will be estimated overall, by symptom category, and by treatment group.

For the analysis of Secondary Objective 3, responses to the satisfaction questionnaire will be summarized overall and by treatment group. Categorical responses will be summarized using contingency tables and/or odds ratios, while continuous responses will be summarized using measures of central tendency such as the mean or median, and measures of dispersion such as the standard deviation or interquartile range.

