### **13.5 Study Records Retention**

Study records and reports including, but not limited to, eCRFs, source documents, ICFs, laboratory test results, and IP inventory records will be retained for 2 years after a marketing application is approved for the IP for the indication for which it is being investigated; or, if no application is to be filed or if the application is not approved for the IP, until 2 years after the investigation is discontinued and the FDA has been notified. These documents will be retained for a longer period, however, if required by local regulations. SICs and EICs for future use will be maintained as long as the sample/specimen exists.

No records will be destroyed without the written consent of the sponsor. It is the responsibility of the sponsor to inform the site PI when these documents no longer need to be retained. The participating sites must contact DMID for authorization prior to the destruction of any study records.

---

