For the analysis of Secondary Objective 1, the time to BV recurrence will be estimated by treatment group using Kaplan-Meier estimates. For participants who experience clinically diagnosed BV recurrence in study by V4, the time of BV recurrence will be defined as the midpoint between the earliest time point of a positive BV diagnosis (post-baseline) and the previous observed time-point. Subjects with BV recurrence diagnosed off study will be treated as missing time to BV recurrence and excluded from the analyses for secondary endpoints, as defined above and in Section 6.5. For participants without BV recurrence at or before V4, the BV recurrence endpoint will be coded as censored, with time to recurrence defined as the elapsed time from the first dose of IP, to the earliest of: V4 time-point, the last observed time-point prior to loss to follow-up, or the time-point at which the participant became ineligible for the particular analysis population.

For the analysis of Secondary Objective 2, the proportion of participants experiencing BV symptoms will be estimated overall, by symptom category, and by treatment group.

For the analysis of Secondary Objective 3, responses to the satisfaction questionnaire will be summarized overall and by treatment group. Categorical responses will be summarized using contingency tables.

Descriptions of the analyses to assess the exploratory objective as well as other analyses that will support the primary and secondary efficacy analyses will be provided in Section 8.4.

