The pseudocode to fit the above analyses is below:

```
proc lifetest method=KM plots=survival(cb=hw test=atrisk) data=dataset outs=surv;
  strata treatment / test=logrank;
  Time time*censor(censored_value);
run;
```

For the Secondary Objective 2, the proportion of participants experiencing vaginal symptoms will be estimated overall, by symptom category, and by treatment group at each visit. See [Table 15](#) for mITT population and [Table 16](#) for PP population. A subject listing of BV symptoms will be presented ([Listing 8](#))

For the Secondary Objective 3, responses to the satisfaction questionnaire will be summarized overall and by treatment group. See [Table 17](#) for mITT population and [Table 18](#) for PP population. Individual subject listings will be presented for all responses to satisfaction questionnaire ([Listing 9](#)).

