14. TECHNICAL DETAILS

SAS version 9.4 or above will be used to generate all TFL.

**15. SUMMARY OF CHANGES IN THE CONDUCT OF THE STUDY OR
PLANNED ANALYSES**

The analyses described in this SAP coincide with the analysis descriptions provided in the study protocol.

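### The daily memory aid, which the protocol names as the source for the symptom endpoint, may be discarded without its symptom entries being transcribed, and the SAP uses clinic-visit answers without declaring the change

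*Protocol*

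**What the plan says.** **Purpose of the aid.** Protocol 3.1: "A simplified participant memory aid will be provided to study participants to document symptoms, AEs, and protocol compliance".

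**Source for the endpoint.** The endpoint in Protocol 3.3.2 names no instrument: "Proportion of participants reporting BV symptoms through the follow-up period". The analysis text in Protocol 10.5.4.2 does name one: "the proportion of participants experiencing vaginal symptoms as assessed by the participant via the daily memory aid will be estimated overall".

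**Disposal.** Protocol 7.1.2, repeated in SAP 4.4.8: "Study personnel may discard the participant's memory aid after documenting compliance". Protocol 13.5, on retention: "No records will be destroyed without the written consent of the sponsor".

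**SAP analysis.** SAP 4.5.1: "the proportion of participants experiencing BV symptoms will be estimated overall, by symptom category, and by treatment group". SAP 8.2: "the proportion of participants experiencing vaginal symptoms will be estimated overall, by symptom category, and by treatment group at each visit". Neither mentions the memory aid. Tables 15 and 16 show abnormal discharge and odor in columns for Visits 0 to 4. Listing 8 shows the same two items for those visits and for early termination.

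**Declared changes.** SAP Section 15: "The analyses described in this SAP coincide with the analysis descriptions provided in the study protocol".

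**The concern.** A participant-reported result that the protocol takes from a daily diary becomes, in the SAP, a set of answers given at clinic visits. The aid serves three purposes, yet it may be thrown away once one of them, compliance, has been documented. A site that follows the text exactly can thus destroy the only day-by-day record of symptoms. The study report would then present visit answers under the protocol's endpoint, with a statement that nothing had changed.

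This matters most for women whose symptoms come and go without a recurrence diagnosis. A woman with two or fewer Amsel criteria at an unscheduled visit continues in the study (Protocol 6.4), and her symptoms at that time have no place in Tables 15–16 or Listing 8. Many of the between-visit symptoms that do reach Table 15 come from visits that end participation, and these overlap with the primary recurrence endpoint. What a separate symptom endpoint would add is the part most exposed to loss.

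**Working it through.** The plan gives no figure to reproduce here. The check is a comparison of texts, followed by an illustration of size.

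**Comparison of texts**

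1. *What must be recorded before disposal.* Protocol 7.1.2 requires adherence to be written on a data collection form, and unused inserts and empty packaging to be counted. It sets no such requirement for symptom entries, and no other section of either document does. Protocol Section 6 defers further instructions to the Manual of Procedures, so a transcription rule may exist there; this cannot be checked.
2. *Whether the SAP tables could still be diary data.* The aid is first issued after randomization (footnote 9 to the Schedule of Events), so the Visit 0 column of Tables 15–16 cannot come from it. The schedule also has a row for the participant's symptom assessment, running from Visit 0 to Visit 4, that is separate from the memory-aid row. The tables match that clinic assessment.
3. *Whether diary symptoms appear elsewhere.* SAP 6.1 promises listings of all data, but none of the 21 listings holds day-level diary symptoms. Listing 15 does hold the study days of insert use. Dosing detail therefore reaches the planned outputs and diary symptoms do not.
4. *Whether the change is declared.* It is not. Protocol 10.5.4.2 names the aid, SAP 4.5.1 and 8.2 leave it out, and SAP Section 15 says the two agree.

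**Illustration of size**

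Inputs from the documents: nominal visit days 29, 57 and 85; 12 weeks of treatment, or 12 × 7 = 84 days.

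Assumptions, none of them in the documents: one episode of D consecutive days, equally likely to start on any of days 1 to 84; all three visits made on the nominal day; a visit question covering that day only; no unscheduled visit.

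For D up to 28, an episode is present on day 29 for D possible start days and on day 57 for another D. It is present on day 85 for D − 1, because a start on day 85 is outside the range. The share seen is (3D − 1)/84.

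- D = 3: 8/84 = 9.5% seen, about 90% missed
- D = 7: 20/84 = 23.8% seen, 76% missed
- D = 14: 41/84 = 48.8% seen, 51% missed
- D = 21: 62/84 = 73.8% seen, 26% missed

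At the other end of the range, suppose the question covers all the time since the last visit. The three visits then span the whole follow-up, and the loss may be near zero apart from recall error. The protocol says only that vaginal symptoms are assessed at each visit, so either reading is possible.

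These are shares of single episodes. The endpoint counts participants, and a woman with several episodes has more chances to be counted.

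**The case against.** The clinic assessment is not an invention of the SAP: it is in the protocol's own schedule, the endpoint definition names no instrument, and Protocol 10.5.4.2 leaves details to the SAP. This stands as far as it goes. Visit answers are a defensible source, but the protocol's analysis text names the diary, and a change of source has to be declared.

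Several stronger readings are tempting, and the documents do not support them.

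- *All between-visit symptoms are lost.* Women who develop symptoms are asked to return (Protocol Section 5). Symptoms may be assessed at unscheduled visits, at the site investigator's discretion (Protocol 6.4), and Table 15 folds in unscheduled visits that end in early termination. The aid is reviewed at Visits 2 to 4, and adverse events are recorded with start and stop dates; Appendix B grades odor, itching and reported discharge. Discarding is permitted, not required.
- *Only three post-baseline snapshots remain.* Listing 8 has an early-termination row, and Table 15 takes in terminating unscheduled visits. Table 37 and Listing 19 also report burning, irritation and itching by visit.
- *Discarding the aid removes the basis for per-protocol compliance, the blinded case review and the Safety Population.* Adherence is recorded before disposal, packaging is counted separately, and Listing 15 carries inserts used and unused with the individual dosing days. The working data survive without the paper form.
- *The discard permission plainly breaches the retention rule.* Protocol 13.5 does not list the memory aid, Protocol 13.1 describes the data collection forms as source, and the permission is in the sponsor's own protocol. Against that, Protocol Section 11 counts as source data the original records of observations needed to reconstruct the trial, and a diary named as an endpoint's source fits that description. The passages need reconciling; a breach is not shown.

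**Conclusion.** The point holds in a limited form. The protocol's named source for Secondary Objective 2 may be discarded with no requirement in these documents to keep its symptom data, the SAP analyses a different source, and SAP Section 15 does not say so. Day-level and transient symptoms that do not lead to termination are outside the planned symptom analysis, and where aids have been discarded they may be unrecoverable.

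A reader might infer that most short episodes are missed. That follows only if the question covers the visit day alone and no unscheduled visit is made: about 90% of 3-day and 76% of 7-day single episodes. With recall since the last visit, the loss may be near zero. The conclusion also assumes that the Manual of Procedures contains no transcription rule. The undeclared change of source does not depend on either assumption.

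The endpoint is secondary and descriptive. The primary analysis, the sample size and its power are not affected.

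**What to change.** 1. Remove the discard permission from Protocol 7.1.2 and SAP 4.4.8, or make it conditional on transcribing the symptom entries, and reconcile it with Protocol 13.5.
2. Retain the aids that still exist and enter their symptom entries in the database. In SAP 8.2, analyse Secondary Objective 2 from them, with the visit answers in Tables 15–16 as supportive.
3. Where aids are gone, report how many per arm, relabel the result as *symptoms reported at clinic visits*, and state the recall window of the visit question.
4. In either case, correct SAP Section 15 so that it declares any change of source.

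The cost is SAP and protocol wording plus some data entry from forms already collected; no new participant procedure is needed. SAP Section 5 records that the study closed early, so a change to the discard rule may protect few further aids. Securing the surviving aids is the urgent step, and items 3 and 4 can be done even if none survive.
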